CCI [REDACTED] This criterion does not apply to the OAV101 group from Period 1 as their anti-AAV9 antibody titers will be elevated after OAV101 treatment.

3. Clinically significant abnormalities in laboratory test results as determined by the Principal Investigator at week 48.
4. Presence of any of the following:
 - An active infectious process requiring systemic therapy intended to eliminate the infection within 30 days prior to the OAV101 administration or sham procedure
 - An active but untreated viral or bacterial infectious process within 30 days prior to the OAV101 administration or sham procedure
 - Febrile illness within 30 days prior to the OAV101 administration or sham procedure
5. Clinical or radiological signs of aspiration within 30 days prior to the OAV101 treatment/sham procedure
6. Hepatic dysfunction (i.e., ALT, TBL, GGT or GLDH, > ULN (i.e., CTCAE grade 1 or greater)) at week 48

NOTE: In the absence of other liver laboratory abnormalities, isolated AST elevation is not considered exclusionary

7. Contraindications for lumbar puncture procedure (including but not limited to cutaneous infection at the treatment site and signs or symptoms of increased intracranial pressure), active administration of any intrathecal therapy, presence of an implanted shunt for the drainage of CSF, presence of an implanted central nervous system (CNS) catheter, or any impediment to CSF access
8. Requiring ventilation for > 16 hours during a 24-hour period or requiring tracheostomy within 30 days prior to OAV101 treatment/sham procedure
9. Awake hypoxemia (defined as O₂ saturation < 95% in room air) within 30 days prior to the OAV101 treatment/sham procedure, that is clinically significant, as per investigator judgement

NOTE: For altitudes > 1000 m, awake hypoxemia is defined as O₂ saturation < 92% in room air

NOTE: For altitudes > 2500m, awake hypoxemia is defined as O₂ saturation < 90% in room air

10. BMI < 3rd percentile, if considered clinically significant by the Investigator

NOTE: BMI is based on the WHO Child Growth Standards ([WHO 2022a](#)) and WHO Growth reference data for 5-19 years ([WHO 2022b](#)).

11. Positive for human immunodeficiency virus (HIV), hepatitis B, or hepatitis C, including latent infections that may be susceptible to reactivation due to corticosteroids.

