5.2 Exclusion criteria

Participants meeting any of the following criteria are not eligible for inclusion in this study.

Retesting of abnormal laboratory and other clinical parameters that could be transient or measurement error may be allowed up to two times based on judgement of the Principal Investigator in communication with the Sponsor Medical Monitor.

1. Excluding SMA, any medical condition considered clinically significant by the Investigator, including cardiomyopathy, hepatic dysfunction, kidney disorder, endocrine disorder including diabetes mellitus, gastrointestinal disorders, metabolic disorders, untreated B6 deficiency, severe respiratory compromise and significant brain abnormalities at either Screening or Baseline that, in the opinion of the investigator, would interfere with the overall interpretation of safety or efficacy of the study.
2. Anti-AAV9 antibody titer reported as elevated (reference to $> 1:50$ or a validated result consistent with being elevated) at Screening **CCI**
[REDACTED]
3. Clinically significant abnormalities in test results during screening period and/or during baseline period as determined by the investigator.
4. Participants will be excluded from the trial for inpatient surgery hospitalization, hospitalization for a pulmonary event, or hospitalization for nutritional support within 2 months prior to Screening and up to Day 1. In addition, patients will not be eligible for the trial if at Screening, inpatient major surgery is planned at any time during the 64-week study. Any other surgeries must not interfere with the ability of the patient to perform the study assessments.
5. Prior injury (e.g., upper or lower limb fracture) or surgical procedure which impacts the participant's ability to perform any of the outcome measure testing required in the protocol and from which the participant has not fully recovered or achieved a stable baseline upon entry into screening period.
6. Contraindications for lumbar puncture procedure, (including but not limited to cutaneous infection at the treatment site and signs or symptoms of increased intracranial pressure), active administration of any intrathecal therapy, presence of an implanted shunt for the drainage of CSF, presence of an implanted central nervous system (CNS) catheter, or any impediment to CSF access.
7. Presence of any of the following:

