 - An active infectious process requiring systemic therapy intended to eliminate the infection within 30 days prior to dosing of OAV101 or the sham procedure
 - An active but untreated viral or bacterial infectious process within 30 days prior to dosing of OAV101 or the sham procedure
 - Febrile illness within 30 days prior to OAV101 administration or sham procedure
8. Administration of vaccines within 2 weeks prior to injection of OAV101 or sham procedure.
9. Clinical or radiological signs of aspiration within 30 days prior to Day 1.
10. Requiring invasive ventilation, awake noninvasive ventilation for > 6 hours during a 24-hour period, noninvasive ventilation for > 12 hours during a 24-hour period or requiring tracheostomy within 30 days prior to Day 1.

11. Awake hypoxemia (defined as O₂ saturation < 95% in room air) within 30 days prior to Day 1.
NOTE: For altitudes > 1000 m, awake hypoxemia is defined as O₂ saturation < 92% in room air
NOTE: For altitudes > 2500 m, awake hypoxemia is defined as O₂ saturation < 90% in room air
12. Hepatic dysfunction (i.e., ALT, TBL, GGT or GLDH, > ULN (i.e., CTCAE grade 1 or greater)) at Screening Visit 1.
NOTE: In the absence of other liver laboratory abnormalities, isolated AST elevation is not considered exclusionary
13. Complications at screening that would interfere with motor efficacy assessments including but not limited to:
 - Presence of severe contractures (e.g., hip flexion contracture) which limits the participant's ability to be positioned in prone for HFMSE item administration
 - Scoliosis with a Cobb angle > 40 degrees in a sitting position, evident on x-ray examination at Screening
14. BMI < 3rd percentile if considered clinically significant by the investigator
NOTE: BMI is based on the WHO Child Growth Standards ([WHO 2022a](#)) and WHO Growth reference data for 5-19 years ([WHO 2022b](#)).
15. History of untreated or uncorrected vitamin deficiencies which can produce sensory neuropathies such as pyridoxine deficiency (B6).
16. Concomitant use of any of the following medication categories within 90 days prior to study treatment (Day 1):
 - Ongoing systemic immunosuppressive therapy (e.g., corticosteroids (except for prophylactic use for OAV101 dosing), cyclosporine, tacrolimus, methotrexate, cyclophosphamide, intravenous immunoglobulin, rituximab), plasmapheresis, immunomodulators (e.g., adalimumab)
17. Inability to tolerate corticosteroids administered by mouth or gastrostomy tube.

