2.1.1 General definitions

Study treatment is OAV101 (1.2x10¹⁴ vector genomes) or sham administration.

The **date of first administration of study treatment** is defined as the date of OAV101/sham administration during Treatment Period 1.

The **date of second administration of study treatment** is defined as the date of OAV101/sham administration during Treatment Period 2.

Study day is the number of days since the date of first administration of study treatment for period 1 and number of days since the date of second administration of study treatment for period 2.

- Study day 1 is the date of the first administration of study treatment during Treatment Period 1 and the date of second administration of study treatment during Treatment Period 2 .
- Study day of date X = date X – date of first administration of study treatment during Treatment Period 1 + 1 if date X is on or after the date of first administration of study treatment during Treatment Period 1.
- Study day of date X = date X – date of first administration of study treatment during Treatment Period 1 if date X is before the date of first administration of study treatment during Treatment Period 1. Study days before the first study treatment administration during Treatment Period 1 will have the prefix “-”.

Baseline is defined as follows:

- **HFMSE**: Baseline value for HFMSE (i.e., total or individual item) score is defined as the average of HFMSE (i.e., total or individual item) score used for stratification (maximum of all available values before baseline visit) and the measurement or evaluation made at the baseline visit prior to the first administration of study treatment during Treatment Period 1, assuming both values have complete and valid scores available. If just one of the above mentioned values (score used for stratification and baseline visit measurement) has a complete and valid score available, then the baseline HFMSE (i.e., total or individual item) score is defined as the single available value.

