- **RULM**: Baseline value for RULM total score is defined as the average of all non-missing assessments prior to the first administration of study treatment during Treatment Period 1, assuming all assessments have complete and valid total scores available. If two of the assessments have a complete and valid total score available, then the baseline RULM total score is defined as average of the two available assessment scores. If just one of the assessments has a complete and valid total score available, then the baseline RULM total score is defined as the single total score available.
- **Other assessments**: The latest non-missing measurement or evaluation made prior to the first administration of study treatment during Treatment Period 1.

Change from baseline is defined as post-baseline value minus baseline value.

For HFMSE and RULM, the **End of Follow-up Period 1** assessment is defined as the average of the Week 48 and Week 52 assessments, assuming both assessments have complete and valid total / individual scores available. If just one of the assessments collected at these two visits has a complete and valid total / individual score available, then the end of Follow-up Period 1

assessment is defined as the single assessment total / individual score collected at Week 48 or Week 52.

Last participation day can be calculated using end of participation date – date of second administration of study treatment + 1.

Inexact values will be handled as follows.

- If a laboratory value is recorded/reported as “>X”, “≥X”, “- If an antibody titer value is reported as <12.5, a value of 0.5×12.5 will be used and if ≥ 819200 is reported, a value of 1.5×819200 will be used for analysis purposes. The originally recorded values will be displayed in corresponding listings.

An **Adverse Event** (AE) is any untoward medical occurrence in a clinical investigation participant, which does not necessarily have a causal relationship with the drug or device under study.

A Treatment Emergent Adverse Event (TEAE) is any AE whose onset or worsening occurred after dosing on Day 1 till the end of follow-up period 2.

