2.1.2 Analysis visit windows

Unless otherwise specified, **analysis visit windows** for efficacy and safety assessments which are summarized on a by-visit basis are defined based on study day post dosing. For by-visit endpoints, the time windows describe how data will be assigned to protocol-specified time points during follow up.

Period 2 windows defined below will be used for analyses of “on or after OAV101 administration” (i.e., OAS).

The analysis windows for respective assessments are as follows:

Vital Signs and Neurological Examination:

Period 1 windows:

Visit	Nominal day	Start day	End day
Day 1	Day 1	Day 1	Day 1
Day 2	Day 2	Day 2	Day 2
Day 3	Day 3	Day 3	Day 3
Week 1	Day 8	Day 4	Day 11
Week 2	Day 15	Day 12	Day 18
Week 3	Day 22	Day 19	Day 25
Week 4	Day 29	Day 26	Day 36
Week 6	Day 43	Day 37	Day 50
Week 8	Day 57	Day 51	Day 64

Visit	Nominal day	Start day	End day
Week 10	Day 71	Day 65	Day 78
Week 12	Day 85	Day 79	Day 99
Week 16	Day 113	Day 100	Day 127
Week 20	Day 141	Day 128	Day 155
Week 24	Day 169	Day 156	Day 183
Week 28	Day 197	Day 184	Day 211
Week 32	Day 225	Day 212	Day 239
Week 36	Day 253	Day 240	Day 267
Week 40	Day 281	Day 268	Day 295
Week 44	Day 309	Day 296	Day 323
Week 48	Day 337	Day 324	Day 351
Week 52	Day 365	Day 352	Week 52 + Day 1 – 1

Period 2 windows:

Visit (OAV-SHAM)	Visit (SHAM-OAV)	Nominal day	Start day	End day
Week 52 + Day 1	Day 1	Day 1	Day 1	Day 1
Week 52 + Day 2	Day 2	Day 2	Day 2	Day 2
Week 52 + Day 3	Day 3	Day 3	Day 3	Day 3
Week 53	Week 1	Day 8	Day 4	Day 11
Week 54	Week 2	Day 15	Day 12	Day 18
Week 55	Week 3	Day 22	Day 19	Day 25
Week 56	Week 4	Day 29	Day 26	Day 36
Week 58	Week 6	Day 43	Day 37	Day 50
Week 60	Week 8	Day 57	Day 51	Day 64
Week 62	Week 10	Day 71	Day 65	Day 78
Week 64	Week 12	Day 85	Day 79	Last participation day

Body Weight:

Period 1 windows:

Visit	Nominal day	Start day	End day
Day 1	Day 1	Day 1	Day 1
Day 2	Day 2	Day 2	Day 2
Week 1	Day 8	Day 3	Day 18

Visit	Nominal day	Start day	End day
Week 4	Day 29	Day 19	Day 43
Week 8	Day 57	Day 44	Day 71
Week 12	Day 85	Day 72	Day 99
Week 16	Day 113	Day 100	Day 127
Week 20	Day 141	Day 128	Day 155
Week 24	Day 169	Day 156	Day 183
Week 28	Day 197	Day 184	Day 211
Week 32	Day 225	Day 212	Day 239
Week 36	Day 253	Day 240	Day 267
Week 40	Day 281	Day 268	Day 295
Week 44	Day 309	Day 296	Day 323
Week 48	Day 337	Day 324	Day 351
Week 52	Day 365	Day 352	Week 52 + Day 1 – 1

Period 2 windows:

Visit (OAV- SHAM)	Visit (SHAM- OAV)	Nominal day	Start day	End day

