The shift tables will cross tabulate the frequency (number and percentage) of participants with baseline versus post-baseline level. These summaries will be presented by laboratory test and treatment group for overall. The shift tables will present shifts from baseline to each visit and to final value. Moreover, for laboratory parameters based on CTC grade, shift tables from baseline to the worst CTC grade level at any time post-baseline will be generated. Participants with specific laboratory abnormalities (defined by CTC grade 3 and 4) will be listed. For laboratory parameters based on Low/Normal/High range, shift tables from baseline to the maximum at any time post-baseline will be generated.

A second set of shift tables will be produced to summarize the shifts from baseline to the maximum value, and final values as well as shift tables based on CTCAE grades from baseline to worst post-baseline values reported after treatment with OAV101. In this second set of outputs, only laboratory values reported on/after OAV101 dosing (during Treatment Period 1 and through the end of study for participants originally randomized to OAV101, during Treatment Period 2 and through the end of study for participants originally randomized to sham administration) will be considered.

The number and percentage of participants meeting each of the following criteria through the end of Follow-up Period 1 will be summarized:

- Alanine aminotransferase (ALT) >2x upper limit of normal (ULN), ALT >3x ULN, ALT >5x ULN, ALT >8x ULN, ALT >10x ULN, ALT >20x ULN
- Aspartate aminotransferase (AST) >2x ULN, AST >3x ULN, AST >5x ULN, AST >8x ULN, AST >10x ULN, AST >20x ULN
- ALT or AST >2x ULN, ALT or AST >3x ULN, ALT or AST >5x ULN, ALT or AST >8x ULN, ALT or AST >10x ULN, ALT or AST >20x ULN

- Total bilirubin $>1.5 \times$ ULN, $>2 \times$ ULN, Total bilirubin $>3 \times$ ULN
- ALT or AST $>3 \times$ ULN and Total bilirubin $>2 \times$ ULN
- ALT or AST $>3 \times$ ULN and Total bilirubin $>2 \times$ ULN and Alkaline phosphatase (ALP) $\geq 2 \times$ ULN
- ALT or AST $>3 \times$ ULN and Total bilirubin $>2 \times$ ULN and ALP $<2 \times$ ULN

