A participant or event will be counted if the post-baseline laboratory values meet the above criteria regardless of the baseline laboratory value (i.e., the post-baseline laboratory value does not need to be worse than the baseline laboratory value). For the last three combination categories, the values do not need to have been collected at the same assessment. For participants meeting any elevation criterion, a corresponding listing of all ALT, AST, ALP, INR, GLDH and total, direct, and indirect bilirubin values will be provided.

Additionally, a summary will be produced to detail the number and percentage of participants with post-baseline, post-OAV101 treatment values meeting the specified criteria outlined above. In this second summary, only laboratory values reported on/after OAV101 dosing (during Treatment Period 1 and through the end of study for participants originally randomized to OAV101, during Treatment Period 2 and through the end of study for participants originally randomized to sham administration) will be considered.

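### The post-OAV101 laboratory shift tables compare sham-then-OAV101 children with a baseline taken about 52 weeks before their OAV101 dose

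*SAP*

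**What the plan says.** **Baseline.** SAP 2.1.1 defines baseline for assessments other than HFMSE and RULM as "The latest non-missing measurement or evaluation made prior to the first administration of study treatment during Treatment Period 1". There is no exception for children who first receive OAV101 in Treatment Period 2.

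**Clock.** The same section restarts study day, as the "number of days since the date of second administration of study treatment for period 2". SAP 2.1.2 adds that "Period 2 windows defined below will be used for analyses of" data on or after OAV101 administration, and relabels the sham-then-OAV101 visits as Day 1, Week 1 and so on.

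**Shift tables.** SAP 2.7.3 plans a second set, covering shifts from baseline to maximum and final values and "shift tables based on CTCAE grades from baseline to worst post-baseline values reported after treatment with OAV101". For children randomized to sham, only Period 2 values enter.

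**Threshold counts.** The ALT, AST and bilirubin counts, including the post-OAV101 version, are made "regardless of the baseline laboratory value (i.e., the post-baseline laboratory value does not need to be worse than the baseline laboratory value".

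**Entry gates.** Protocol 5.2 (criteria 12 and 25) and the Period 2 eligibility list in Protocol Section 3 (criteria 6 and 12) exclude ALT, total bilirubin, GGT or GLDH above ULN and platelets below LLN. They apply at Screening Visit 1 (platelets: at screening) and again at Week 48. Both liver criteria carry the same note: "In the absence of other liver laboratory abnormalities, isolated AST elevation is not considered exclusionary". Neither list sets a numeric limit for ALP or troponin I. The remaining check is the investigator's judgement: "Clinically significant abnormalities in test results during screening period and/or during baseline period as determined by the investigator" at entry and "Clinically significant abnormalities in laboratory test results as determined by the Principal Investigator at week 48" before Period 2.

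**The concern.** The plan moves the clock to the OAV101 dose for sham-then-OAV101 children but leaves the reference value where it was. A post-OAV101 shift table is read as showing what changed after the product was given. For these children it shows what changed after a year of sham follow-up plus the product.

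The reference matters more here than in the Period 1 tables. In Period 1 a concurrent sham arm shows what happens without OAV101. After the Period 2 dose every eligible child has had OAV101, so the pre-dose value is the main means of telling a new change from an old one. The shift tables are also the only summary named in SAP 2.7.3 that sets values after the Period 2 dose against a reference: the change-from-baseline summaries and box plots there stop at the end of Follow-up Period 1, and the threshold counts use no reference.

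**Working it through.** **1. Who is affected.** SAP 2.7.3 states no figure, so the counts come from the design. With 125 children randomized 3:2, 125 × 3/5 = 75 receive OAV101 first and 125 × 2/5 = 50 receive sham first, matching SAP Section 3. (The stated power of about 90% for these arm sizes reproduces at 90.8%; nothing here turns on it.)

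- All sham children dosed in Period 2: 50/125 = 40% of OAV101-treated children.
- Five not dosed because of anti-AAV9 antibodies (the protocol's upper estimate): 45/120 = 37.5%.

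**2. How old the reference is.** Nominal days are from Protocol Table 8-1. The Period 2 dose is on Day 366 and there is no Day 0, so age = 366 − reference day, less 1 if the reference day is negative.

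| Reference value | Day | Age at Period 2 dose |
|---|---|---|
| Baseline visit | −1 | 366 days (52.3 weeks) |
| Screening Visit 1 | −60 to −45 | 410 to 425 days (58.6 to 60.7 weeks) |
| Week 48 | 337 ± 7 | 22 to 36 days |
| Week 52 | 365 | 1 day |

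The first row assumes chemistry is drawn at the baseline visit, which the public schedule does not show. As far as Table 8-1 can be read, troponin I is measured before treatment only at Screening Visit 1, so the second row applies to it. Later values are planned: the SAP 2.1.2 chemistry and hematology windows include Weeks 48 and 52, and the Week 48 troponin I window runs to the day before the Period 2 dose.

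**3. What the old reference does.** Three hypothetical sham-first children:

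| Child | Period 1 baseline grade | Week 48/52 grade | Worst grade after OAV101 | Planned table | Last pre-OAV101 reference |
|---|---|---|---|---|---|
| A | 0 | 1 | 1 | 0 to 1: shift | 1 to 1: no shift |
| B | 1 | 0 | 1 | 1 to 1: no shift | 0 to 1: shift |
| C | 0 | 0 | 1 | 0 to 1: shift | 0 to 1: shift |

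The error can go either way. For OAV101-first children the last two columns coincide by definition.

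**4. Which analytes.** For ALT, total bilirubin, GGT, GLDH and platelets, the gates ordinarily place a child in row C's pattern: normal at both references. Retesting is allowed, and a value can change between the gate and the dose, so this is usual rather than certain. AST, ALP and troponin I all feature in the SAP 2.7.3 shift tables without a numeric gate, so patterns A and B are possible.

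**5. Illustrative size.** The documents give no AST, ALP or troponin I distribution at entry or at Week 48. Let *s* be the assumed share of sham-first children in pattern A for one analyte. Children affected = (number sham-first) × *s*. Points in a pooled column = 100 × that count / (number OAV101-treated).

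| Assumed *s* | Of 50 | Points of 125 | Of 45 | Points of 120 |
|---|---|---|---|---|
| 0% | 0 | 0 | 0 | 0 |
| 2% | 1.0 | 0.8 | 0.9 | 0.75 |
| 5% | 2.5 | 2.0 | 2.25 | 1.9 |
| 10% | 5.0 | 4.0 | 4.5 | 3.75 |

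The points columns apply only if the two sequences share a column.

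**The case against.** **The baseline does precede OAV101 for everyone.** This is correct. A reader might infer that the post-OAV101 tables have no pre-OAV101 reference. The documents do not support that: the Period 1 baseline always comes before OAV101, and for the 75 OAV101-first children it is the right value.

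**Sham-year drift is already tabulated.** The first shift tables show shifts to each visit by treatment group, so the sham arm's grades at Weeks 48 and 52 will be in the report. This is useful context, but it is marginal: a group table does not link a child's pre-dose grade to that child's grade after OAV101.

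**Listings allow recovery.** Children who meet a hepatic elevation criterion have all their liver values listed, and out-of-range chemistry values are listed too. Individual cases can be traced, but the summary table stays as it is.

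**Pooling is not stated.** SAP 2.7.3 does not say that the two sequences share a column in the post-OAV101 laboratory tables. SAP 2.2 analyses the OAV101-treated set by assigned treatment, and explicit combining language appears only for concomitant medications in SAP 2.4.2. This stands, so the dilution figures above are conditional. Separate columns would make the sham-first children visible but would not change their reference.

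**Consistency.** The post-OAV101 ECG outputs in SAP 2.7.4.1 appear to rest on the same fixed baseline, so changing laboratory tables alone leaves two conventions in the safety section. This is a fair cost and calls for a footnote. The updated baseline in SAP 5.6 is weak precedent, since it concerns an 18th birthday. It does show that the SAP writes out a re-anchored baseline where it wants one.

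**Conclusion.** The point holds in a narrow form. As written, the second laboratory shift tables compare up to 50 of 125 OAV101-treated children (or 45 of 120) with a value about 52 weeks before OAV101, and shifts can be misclassified in either direction. The exposed analytes are those without a numeric Week 48 gate, such as AST, ALP and troponin I. The size is unknown and may be nil, because every rate used above is an assumption. The tables are descriptive; no test, power or alpha figure changes. This is an optional improvement.

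A reader might also infer that the AST and ALT-or-AST threshold counts are wrong because they ignore baseline while isolated AST elevation is admitted, or that the bilirubin-combination rows share the fault. The documents do not support either as a defect. Counting any qualifying value is an explicit choice, and its error is an over-count rather than a missed case. Pre-existing elevations are expected to balance between the randomized arms in Period 1, and grade shifts and full listings back up the counts. New-onset AST rows or a flag on the combination rows would be a matter of preference.

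**What to change.** Add one sentence to SAP 2.7.3: for the post-OAV101 laboratory shift tables, baseline is the last non-missing value before OAV101 dosing. For sham-then-OAV101 participants, this is the last value before the Week 52 + 1 Day dose, normally from Week 52 or Week 48. Leave the Period 1 shift tables and the any-value threshold counts as they are.

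The cost is that sentence plus one extra derived value per laboratory parameter for sham-first participants, from data already planned for collection. The downside is that these participants carry two baselines, so each affected table needs a footnote saying which one it uses.
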